6.8 Outcome Variables

- VO₂peak Test
 - VO₂peak
 - Peak Power
- INT and TTE Protocol
 - Peak Power
 - Average Power
 - RPE
 - Total time to exhaustion at 90% VO₂peak
- Anthropometrics
 - Height
 - Weight
 - Age
 - Body Fat Percentage
- HRV
 - Root mean square of the successive differences of R–R intervals (RMSSD)
- Sweat Rate Determination
 - Individual sweat rate pre-post exercise

7.0 Data and Specimen Banking*

7.1 Data Storage.

All informed consents, medical history questionnaires and screening paperwork will be stored in a locked cabinet in the Physiology of Work and Exercise Response (POWER) Laboratory, and data collection sheets will be stored in a locked cabinet in the Kinesiology and Teaching Laboratory during and following the investigation; all electronically entered data will be saved in an encrypted file. Data from VO₂peak tests and performance tests will be collected and managed using Trueone 2400 software on a secure computer. The computer is password-protected, and the data stored is deidentified and password protected.

Participant folders will be marked with an ID number to protect against a breach of confidentiality; participant names

and ID numbers will be stored separately in a digitally encrypted file.

7.2 Data Access.

Access to research-related data, paperwork, and records will be limited to appropriate laboratory personnel only.

7.3 Data disposal.

All participant records and paperwork (e.g., informed consent forms, data collection sheets) will be destroyed six years from the end of the study. Password protected electronic file containing participants' names will be discarded after the completion of data analysis.

7.4 Data dissemination

The results of this study will be published as a group as part of a scientific publication. No individual results will be published or shared with any third person or party.

8.0 Sharing of Results with Subjects*

8.1 Individual results will remain confidential and will only be relayed to the participant upon request. All information attained from the medical history questionnaire will be held in strict confidence.

9.0 Study Timelines*

9.1 Describe:

- All visits will be separated by 48-72 hours. Visit #1 and Visit #2 will take approximately 60-90 min each. Visit #3 will take approximately 4 hours.
- We anticipate the participant recruitment and enrollment will be completed within two months and estimate that data collection will be completed within approximately 6 to 8 months.
- The estimated date for completion of primary analysis will be December 2021.

10.0 Inclusion and Exclusion Criteria*

10.1 Individuals will be screened for eligibility using the American College of Sports Medicine Exercise Preparticipation Health Screening Questionnaire for Exercise Professionals (PHSQEP), Physical Activity Readiness Questionnaire for Everyone (PAR-Q+), and confidential Medical Health and Activity Questionnaire to determine the need for medical clearance from a health care professional. Participants presenting

any sign or symptoms suggestive of cardiovascular, metabolic, or renal disease will be asked to seek medical clearance in order to participate.

10.2 Inclusion Criteria.

- Men between the ages of 35 and 59 years
- Free of any physical limitations as determined by the Exercise Preparticipation Health Screening Questionnaire for Exercise Professionals (PHSQEP), and a Physical Activity Readiness Questionnaire for Everyone (PAR-Q+)
- Regularly engaged in endurance exercise (running, cycling, swimming) for a minimum of three years, a weekly training volume of 5-10 hours, and a maximal oxygen uptake of $45.00 \text{ ml}\cdot\text{kg}^{-1}\cdot\text{min}^{-1}$ or higher as determined by completion of $\text{VO}_{2\text{peak}}$ assessment (Visit #1).

10.3 Exclusion Criteria

- Recent musculoskeletal injuries or surgeries
- Any chronic illness that requires continuous medical care
- Current incarceration, cognitive impairment or inability to provide consent
- Present or past use of performance-enhancing drugs

10.4 Indicate specifically whether you will include or exclude each of the following special populations:

- Adults unable to consent: exclude
- Individuals who are not yet adults (infants, children, teenagers): exclude
- Pregnant women: exclude
- Prisoners: exclude

11.0 Vulnerable Populations*

11.1 N/A: This research does not involve any vulnerable populations.

- No pregnant women will be included.
- No prisoners will be included.
- No children will be included.
- No cognitively Impaired Adults will be included.

12.0 Local Number of Subjects

12.1 All participants will be recruited from the University of Central Florida and from within the surrounding Central Florida area.

12.2 Participants will be recruited and screened until a maximum of 50 individuals are enrolled. Participants will be considered enrolled only after an informed consent document has been signed, a medical history questionnaire, PHSQEP and PAR-Q+ have been completed, and anthropometric data have been recorded. To account for individuals who do not meet the inclusion criteria, the number of recruited individuals will likely exceed the number of enrolled participants. However, no more than 50 participants will be recruited.

13.0 Recruitment Methods

13.1 Participants will be recruited at the University of Central Florida and in surrounding locations through flyers, posters, information sheets, notices, and internet postings and media to recruit participants. The flyer will be posted on social media. Participant recruitment will begin upon approval of the IRB protocol and all supporting documents.

13.2 Subjects will primarily be recruited from the University of Central Florida and surrounding locations. Participants will be eligible to participate if they hear about the study through flyers, posters, information sheets, notices, internet postings, and/or media, and word of mouth.

13.3 Participants will be recruited by flyers, posters, information sheets, notices, and internet postings, which will detail the study objectives and a brief explanation of the inclusion and exclusion criteria.

13.4 There will not be any compensation to participants for participating in this study

14.0 Withdrawal of Subjects*

14.1 Participants have the right to discontinue participation without penalty, regardless of their status in the study. Participants will also be instructed that participation in the study may be terminated at any time by the researchers in charge of the project. Possible reasons for subject withdrawal without their consent include inability or unwillingness to adhere to the study protocol, failure to adhere to any requirements (including exercising vigorously within the 24-hours prior to the testing visit), and refusal to participate in testing trials

14.2 If a participant is asked to withdraw without their consent, they will be told that they can no longer participate in the study and the reasoning for this will be explained privately. Additionally, study personnel will explain the destruction of their data to them.

14.3 If a participant is asked to withdraw or voluntarily withdraws from the study, their data will be removed from the study results and destroyed.

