- Visit #2: Participants will report to the testing location for familiarization to the testing protocols. Based on VO₂peak data obtained during Visit #1, participants will perform the INT and TTE protocol outlined in section 6.4 to familiarize them with the protocol for the experimental trial (Visit #3), and teach them how to respond to the rating of perceived exertion RPE measures.
- Visit #3: To ensure participants are hydrated prior to the start of testing, they will be asked to consume 500 ml of water 2 hours before their arrival to the laboratory for testing (Moreno et al. 2013; Vanderlei et al. 2015). Participants will complete a warm-up followed by the INT and TTE protocol, as outlined in section 6.4. Immediately following the INT and TTE testing, the participant will be given an isocaloric CHO (1.2 g/kg of bw), CHO-P (0.8 g/kg bw CHO + 0.4 g/kg bw protein), or PLA beverage that have a similar appearance and taste and will be blinded to the contents. Participants will rest for two hours and then repeat the INT and TTE testing (6.4). Participants will be weighed in their cycling bib shorts immediately before and after the first and second bouts of INT exercise and TTE testing. Sweat rate will be determined based on the difference between pre-and post-weight changes for each bout of exercise, the amount of fluid consumed during the recovery period, and total exercise time in minutes (Casa 2019). Participants will also be asked to report total sleep in number of hours and minutes for the night prior to testing. Immediately upon completion of the second exercise bout, participants will rest for an additional 30 minutes for HRV recording. Completion of Visit #3 will conclude all required testing.

6.2 Anthropometric measurements:

- Participants will be assessed for body weight, height, and body composition.

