6.4 High-Intensity Aerobic Intervals and Time to Exhaustion

- All participants will warm-up on a cycle ergometer for 3-minutes at 50W, 2-minutes at 100W, and 1-minute at 75W followed by a 3-minute rest. Participants will then perform 5 x 4-minute high-intensity aerobic intervals at 70-80% of individual PPO, as determined by the familiarization trial. Two-minutes of low-intensity cycling at 50W will separate intervals. Immediately following the fifth interval, participants will cycle at a work rate (watts) that corresponds to 90% PPO until volitional exhaustion or when rpm falls below 60 for 10 seconds. Following the endurance trial (INT and TTE), participants will cycle with no resistance for 5 minutes to cool down. Revolutions per minute will be the only performance measure visible to participants, and minimal verbal encouragement will be provided throughout the aerobic intervals and time to exhaustion. Rating of perceived exertion (RPE) will be recorded using the Borg 10 scale during the last 30 seconds of each aerobic and rest interval and once immediately before completion of the TTE.

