15.0 Risks to Subjects*

15.1 The exercise-based assessments carry the same inherent risks as participating in any physical activity, such as muscle soreness, and fatigue and possibly muscle strains, and/or joint sprains, elevated heart rate, feelings of nausea and possible episodes of emesis, arrhythmia, myocardial infarction, and death. To minimize these risks, participants will be instructed on the appropriate technique for the performance assessments and will be required to complete a warm-up prior to completing the assessments. Furthermore, participants will be informed that they can quit at any time before or during the test. All personnel involved in this study are CPR certified. Furthermore, all research personnel involved in data collection are experienced in the administration of the proposed assessments, and all Doctoral students involved in this study are Certified Strength and Conditioning Specialists through the National Strength and Conditioning Association. Participants will be instructed to immediately stop and report any injury or discomfort associated with the performance assessments to a member of the investigative team. The extent of the injury/discomfort, as well as the ability of the participant to continue with the study, will be subsequently be determined by the investigative team. If it is deemed that the discomfort/injury will prevent the participant from completing the study, or if the injury/discomfort may be exacerbated by further participation in the study, the investigative team will suspend the individual's participation in the study.

15.2 This study is recruiting for male participants only. Therefore, subjects who are pregnant will not be enrolled.

15.3 There are no risks to others in the study who are not participants.

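### Section 14.3 destroys the data of any man who withdraws, even after his randomised drink, so drink-related losses can leave both the analysis and the record

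*Combined protocol and SAP*

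**What the plan says.** Section 14.3 gives the rule: "If a participant is asked to withdraw or voluntarily withdraws from the study, their data will be removed from the study results and destroyed". Section 14.2 confirms it for men whom the team withdraws: "study personnel will explain the destruction of their data to them". Neither section sets a limit by visit, randomisation or receipt of the drink.

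Section 14.1 lets a man leave whatever his stage in the study and lets the researchers end his participation at any point. On the second route it says: "Possible reasons for subject withdrawal without their consent include inability or unwillingness to adhere to the study protocol". It also lists "refusal to participate in testing trials".

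Section 6.1 (Visit #3) sets the order of events. The drink follows the first intervals and TTE, and then: "Participants will rest for two hours and then repeat the INT and TTE testing". A further 30 minutes of rest for HRV recording comes after bout 2. In section 6.4 each bout is five intervals followed by a ride at 90% of peak power "until volitional exhaustion or when rpm falls below 60 for 10 seconds".

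Section 17.1 plans a one-way ANCOVA for TTE, HRV slope and sweat rate, with the pretest as covariate. It defines no analysis set and does not say how a man without a bout-2 TTE is handled or reported.

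**The concern.** Section 2.1 asks how the drink affects the next bout of exercise. Bout 2 comes after the randomised drink, so removing men because of what happened between the drink and the end of Visit #3 can undo the balance that randomisation gave. If men who recover badly on placebo are removed, a real carbohydrate benefit looks smaller. If a drink upsets some men and they are removed, that drink looks better tolerated than it was. TTE is the only performance measure with a planned test, and the target is 6 men per arm (section 17.2), so one man is a sixth of an arm.

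Destruction goes further than exclusion. An excluded man can still be counted by drink and reason and used in a sensitivity analysis. Once his data are destroyed, that is much harder.

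**Working it through.** **Who is exposed.** The sections above, read in order of events at Visit #3, give five cases.

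| What happens after the drink | Bout-2 TTE exists? | Position under the current text |
|---|---|---|
| Leaves during the 2-hour rest, or declines bout 2 | No | Withdrawal or refusal under 14.1; data destroyed under 14.3 |
| Cannot finish the second intervals | No; 6.4 gives no score | Can be treated as inability to adhere under 14.1, then 14.3 |
| Rides the TTE, then leaves before the HRV recording ends | Yes | If counted as a withdrawal, a valid TTE is destroyed |
| Suspended by the team for symptoms (15.1) | Depends on timing | 15.1 is silent on data; the link to 14.3 is an inference |
| Reaches the TTE and stops through exhaustion or low cadence | Yes | A valid result under 6.4; he stays in |

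**Inputs for the size.** The documents give no TTE mean, SD or rate of loss after the drink, so the plan has no figure to reproduce here. Section 17.2 recruits 30 to complete 18, a margin of 12/30 = 40%. That is not the post-drink rate. Section 12.2 says "Participants will be considered enrolled only after an informed consent document has been signed", together with the screening forms and body measurements, and enrolment therefore comes before the VO₂peak test that settles eligibility.

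**Assumptions.** Three arms of 10; bout-1 to bout-2 correlation 0.7; ANCOVA on drink and bout-1 TTE; omnibus F test at 0.05. Results are in units of the adjusted (residual) SD. The 1 or 2 men deleted from one arm are those lowest on a liability to stop, whose correlation with bout-2 recovery is 1 (full overlap), 0.5 (half) or 0 (none).

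**Check by order statistics, full overlap.** In 10 standard normal values, the lowest has expected value −1.539 and the lowest two sum to −2.540. The overall mean is 0, so the mean of those left rises by:

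- 1 deleted: 1.539/9 = 0.17 SD
- 2 deleted: 2.540/8 = 0.32 SD

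**Simulation, deletion in the placebo arm only.** Each cell gives the result for 1 / 2 men deleted. The last two columns assume a true 1-SD benefit of both active drinks.

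| Overlap | Shift, no true effect (SD) | False-positive rate | Estimate of a true 1-SD benefit | Omnibus power |
|---|---|---|---|---|
| No deletion | 0 | 0.05 | 1.00 | 56% |
| Full | 0.17 / 0.32 | 0.07 / 0.10 | 0.83 / 0.68 | 42% / 29% |
| Half | 0.09 / 0.16 | 0.06 / 0.06 | 0.91 / 0.84 | 46% / 37% |
| None | 0 / 0 | 0.05 / 0.05 | 1.00 / 1.00 | 53% / 49% |

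The fall in power with no overlap comes only from having fewer men. Correlations of 0.5 or 0.9 between bouts leave the full-overlap shifts and false-positive rates essentially unchanged. Nearer the target of 18, deleting the worst 1 of 7 placebo men gives a shift of 0.23 SD and a false-positive rate of 0.07.

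**Balanced losses.** With 1 or 2 men deleted in every arm, the bias in the contrast is about 0.00 SD at every overlap. The false-positive rate is about 0.05 to 0.06 at half or no overlap and 0.08 to 0.10 at full overlap.

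**The case against.** The strongest objection is that the fix does little for the men most clearly exposed. A man who goes home during recovery or declines bout 2 has no bout-2 TTE, so he is absent from the main ANCOVA whether or not his other data are kept. This stands. The table shows the harm of drink-related loss in general; changing 14.3 removes it only for men who have a bout-2 TTE.

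The illustration also puts every loss in one arm, at 10% or 20% of that arm, and nothing in the documents supports such a rate. This stands too. Balanced or unrelated losses leave the contrast unbiased, and the window is one visit on one day. Double-blinding limits deliberate selection by arm, but it does not prevent losses that the drink itself causes.

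A reader might infer that nobody could ever check losses by drink. The documents do not support that. Adverse events are reported to the IRB (18.1, 20.1), and 14.3 does not say that those reports or the allocation list are destroyed. However, such reports need not capture a man who simply leaves, and they are not a source of performance data.

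A reader might also infer that men suspended under 15.1 are always deleted. That section applies "If it is deemed that the discomfort/injury will prevent the participant from completing the study", or if further participation could make the problem worse. It says nothing about their data.

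In the other direction, the six-year retention text in 7.3 and 17.3 does not rescue the data. It is general, and 14.3 is the specific rule for men who withdraw.

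**Conclusion.** The point holds as a defect of retention and reporting, with a possible but unsized bias in the TTE contrast. As written, 14.1 to 14.3 allow the data of a man already given his drink to be removed and destroyed for a reason related to that drink, and 17.1 provides nothing that would show it.

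The shifts of 0.17 and 0.32 SD, with false-positive rates of about 0.07 and 0.10, are the full-overlap results. They rest on assumed losses of 1 or 2 of 10 men in a single arm. Half overlap gives 0.09 and 0.16 SD with a rate of about 0.06, and no overlap gives no bias.

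Two stronger readings fail. The documents do not show that drink-related losses will occur, and the 40% recruitment margin is no evidence of them. Nor does the rule delete everyone who rides poorly in bout 2, because a short TTE ended by exhaustion or low cadence is a valid result.

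**What to change.** 1. In 14.2 and 14.3, destroy data only when the participant asks for it. Otherwise keep everything collected up to withdrawal.
2. In 17.1, run the TTE ANCOVA on every man given his assigned drink who started the bout-2 TTE, by assigned drink, whether or not he later withdrew. Use the time actually ridden at 90% of peak power.
3. Count men who do not start the bout-2 TTE, including those who stop in the second intervals, as having no TTE. Report them by drink and reason. Add a rank-based ANCOVA as a sensitivity analysis, giving the worst rank to symptom-related failures only and not to causes such as equipment failure.
4. Add one data-sheet field for when and why bout 2 ended or was not started.

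For men with no bout-2 TTE the main contrast stays as it is; their loss is made visible and tested in the sensitivity analysis.

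**Cost.** An IRB amendment, a consent-form change if that form repeats the promise to destroy data, a few sentences in 17.1 and one field. There are no added visits or participants. The change should be in place before Visit #3 data accumulate, because destroyed records cannot be restored.

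**Downside.** Symptom-shortened rides add spread. If one man per arm keeps a ride shortened by a further 1 SD (assumed), omnibus power for a 1-SD benefit is 37 to 53%, against 51 to 64% if he is deleted, and the false-positive rate is 0.015 to 0.036. This scenario has one man in every arm, so it cannot be netted against the one-arm table above. With one failure per arm, the worst-rank analysis has about 18 to 24% power, which is why it is only a sensitivity analysis. Scoring failures as 0 s in the main ANCOVA is not proposed: with 0 s assumed to lie 3 SD below the placebo mean, power is about 8 to 9%.

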15.0 Risks to Subjects*

15.1 The exercise-based assessments carry the same inherent risks as participating in any physical activity, such as muscle soreness, and fatigue and possibly muscle strains, and/or joint sprains, elevated heart rate, feelings of nausea and possible episodes of emesis, arrhythmia, myocardial infarction, and death. To minimize these risks, participants will be instructed on the appropriate technique for the performance assessments and will be required to complete a warm-up prior to completing the assessments. Furthermore, participants will be informed that they can quit at any time before or during the test. All personnel involved in this study are CPR certified. Furthermore, all research personnel involved in data collection are experienced in the administration of the proposed assessments, and all Doctoral students involved in this study are Certified Strength and Conditioning Specialists through the National Strength and Conditioning Association. Participants will be instructed to immediately stop and report any injury or discomfort associated with the performance assessments to a member of the investigative team. The extent of the injury/discomfort, as well as the ability of the participant to continue with the study, will be subsequently be determined by the investigative team. If it is deemed that the discomfort/injury will prevent the participant from completing the study, or if the injury/discomfort may be exacerbated by further participation in the study, the investigative team will suspend the individual's participation in the study.

15.2 This study is recruiting for male participants only. Therefore, subjects who are pregnant will not be enrolled.

15.3 There are no risks to others in the study who are not participants.

16.0 Potential Benefits to Subjects*

16.1 There is no direct benefit of participation in the study.

17.0 Data Management* and Confidentiality

17.1 All statistical analyses will be conducted via the Statistical Package for Social Science (SPSS) software for Windows version 21 (SPSS Inc., Chicago, IL). Data will be statistically analyzed using separate 1-way analysis of covariance (ANCOVA) for TTE, HRV-Slope Recovery, and Sweat Rate measures. The pretest and

the posttest values will be used as a covariate and dependent variable, respectively. If the ANCOVA is significant, Fisher's LSD Post-Hoc analysis will be used to determine group differences. For effect size (ES), the partial eta squared statistic will be reported, with 0.01, 0.06, and 0.14 representing small, medium, and large ES, respectively. The significance level will be set at $p \leq 0.05$.

17.2 The calculation of sample size (G*Power 3.1.9.4) was based on pilot data in low-to-moderately trained young men (22.1 + 3.2 years) collected in our lab using the same protocol (90% PPO TTE) as outlined in this study. The total sample size was determined to be a total of 18 (6 in each group) based on a one-way ANCOVA, power of 0.90, and an alpha of 0.05. However, due to potential dropout rates, a total of 30 participants (10 per group) will be recruited with the goal of completing 18.

17.3 Individual results will remain confidential and only be related to the participant upon request once the study is completed. All questionnaires and data collection sheets will be kept in a locked cabinet during and following the study. Data that is electronically stored will be kept on a password-protected computer in the office of the investigator who oversees data collection. All information will be destroyed six years from the end of the study. Participant folders will be marked with an I.D. number to protect against a breach of confidentiality. Participant names and I.D. numbers will be stored apart from the subject folders in a password protected electronic file.

17.4 Quality control of collected data will be performed by ensuring all data files remain in filing cabinets when not in use.

17.5 Participant folders and other data will be kept in a locked filing cabinet and stored on a computer whose files are encrypted with a password. Further, all identifiable information will be stored separately from any data collection sheets; Computer file containing participants' names will be discarded upon completion of data analysis. Only study personnel will have access to data. All signed consent forms will be stored separately from the rest of the data and will be held for a minimum of 5 years after completion of the study.

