6.0 Procedures Involved*

6.1 To test the hypothesis, this study will utilize a randomized, double-blind, placebo-controlled between-subject design to examine the effects of CHO and CHO-P supplementation on short-term recovery following aerobic interval exercise and time to exhaustion testing in MCA's. After completing the informed consent and screening process (Visit #1), each participant will be assessed for their anthropometric measures as well as body composition and will complete a GXT to volitional exhaustion on a cycle ergometer to determine VO₂peak. Participants will also be provided with the option to return to the lab on a separate date for the GXT and VO₂peak testing. Forty-eight to 72 hours after Visit #1, or VO₂peak testing, participants will return to the lab for familiarization with the INT exercise protocol and TTE (Visit #2). Within five to nine days after familiarization (Visit #2), participants will return to the lab for Visit #3 to complete INT exercise and TTE, a 2-hour passive recovery period including the consumption of one of three treatments (CHO, CHO-P, PLA), followed by repeated INT exercise and TTE, HRV and SR determination. Participants will also complete the Nutritional Recovery Practices, Knowledge, and Beliefs of Australian Triathletes survey during the 2-hour recovery period. Participants will be asked to complete the ASA24®, an automated self-administered 24-hour dietary assessment tool during the 5-9-day period between familiarization (Visit #2) and the experimental protocol (Visit #3).

Testing Procedures.

- Participants will report to the testing location on 3 separate occasions.
- Visit #1: The study will be explained to the participant by the investigators. Participants will be asked to provide their written, informed consent. The participants will then be asked to complete the American College of Sports Medicine Exercise Preparticipation Health Screening Questionnaire for Exercise Professionals (PHSQEP), Physical Activity Readiness Questionnaire for Everyone (PAR-Q+), and Medical Health and Activity Questionnaire.

Following the written consent and screening process, anthropometrics and body composition will be measured, and the VO₂peak test outlined in section 6.3 will be completed. Following informed consent, screening, and anthropometrics and body composition, if necessary (i.e., due to time constraints), participants may choose to return to the lab on a separate occasion for VO₂peak testing.

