6.5 Recovery Slope of Heart Rate Variability

- R-R intervals recorded via the heart rate monitor and Elite HRV will be downloaded and analyzed using a laptop with commercially available HRV analysis software (Kempele, Finland; Kubios HRV Analysis v 3.3, Kuopio, Finland). R-R interval series will be filtered using the software's automatic artifact correction to detect and replace artifacts from the normal sinus arrhythmia. Replaced R-R periods will not exceed 5% of total heartbeats. Each window will be analyzed for the time-domain values of root mean square of the successive differences of R-R intervals (RMSSD). RMSSD reactivation following exercise will be reported to behave linearly during the first 30-minutes post-exercise (Orellana et al. 2019). Therefore, RMSSD values will be recorded during the 90% TTE and then post-exercise every 5 min. Using

simple linear regression, a slope value for RMSSD values vs. time of recording (end of TTE, 5min, 10min, 15min, 20min, 25min, 30min) for each participant will be performed.

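### Section 17.1 needs a pretest HRV slope as covariate, but none is scheduled before the drink, so the ANCOVA either has no covariate or adjusts for a largely post-drink measure

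*Combined protocol and SAP*

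**What the plan says.** Section 17.1 sets one rule for three outcomes: "Data will be statistically analyzed using separate 1-way analysis of covariance (ANCOVA) for TTE, HRV-Slope Recovery, and Sweat Rate measures". The next sentence assigns the roles: pretest and "posttest values will be used as a covariate and dependent variable, respectively". No exception is made for HRV slope.

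Section 6.5 defines the slope by regressing RMSSD on time: "RMSSD values will be recorded during the 90% TTE and then post-exercise every 5 min". It uses seven points, from the end of TTE to 30 minutes, and names no bout or visit.

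Section 6.1 gives the schedule:
- The design summary places HRV after the recovery period and drink: "followed by repeated INT exercise and TTE, HRV and SR determination".
- At Visit #3 the drink comes straight after bout 1: "Immediately following the INT and TTE testing, the participant will be given an isocaloric CHO (1.2 g/kg of bw".
- The one HRV rest described at Visit #3 comes after bout 2: "Immediately upon completion of the second exercise bout, participants will rest for an additional 30 minutes for HRV recording".
- At Visit #2, "participants will perform the INT and TTE protocol outlined in section 6.4 to familiarize them with the protocol"; no HRV recording is listed.

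Section 17.2 gives the sample: "a total of 30 participants (10 per group) will be recruited with the goal of completing 18".

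**The concern.** An ANCOVA covariate should be measured before the randomized treatment can affect it. TTE and sweat rate meet this requirement: bout 1 is completed before the drink, and body weight is taken around both bouts. HRV recovery slope is different because it describes the half hour after exercise, and the drink is given at the start of that half hour.

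If no first-bout slope is recorded, a planned analysis lacks its covariate and the replacement would be chosen after data collection. If a first-bout slope is recorded and used, the adjusted comparison can be attenuated, inflated or reversed, depending on what the drink does to early recovery. HRV slope is in no objective or hypothesis, so the performance conclusions are not at stake. It is, however, a listed outcome (6.8) and one of only three for which 17.1 names a test.

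**Working it through.** The plan gives no figure for HRV slope to reproduce. The check sets the schedule against the time of the drink, then works out what adjustment for a post-drink covariate would do.

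**Step 1: is there a pre-drink value?**

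| Outcome | Pre-drink value | Post-drink value |
|---|---|---|
| TTE | bout 1, Visit #3 | bout 2 |
| Sweat rate | weights around bout 1 | weights around bout 2 |
| HRV slope | none scheduled | 30 min after bout 2 |

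**Step 2: could a bout-1 slope serve?** The points are 0, 5, 10, 15, 20, 25 and 30 min after TTE. With the drink given at the end of TTE, 1 of 7 precedes it and 6 of 7 fall at or after it. If the drink follows the 5-minute cool-down of section 6.4, the count is 5 or 6 of 7. A regression slope weights each point by its distance from the mean time of 15 min (15, 10, 5, 0, 5, 10, 15; sum 60). The end-of-TTE point therefore carries 15/60 = 25% of the absolute weight and the later points 75%.

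**Step 3: what would ANCOVA estimate?** Let d1 and d2 be the drink effects on the bout-1 and bout-2 slopes, and b the within-group coefficient. The expected adjusted difference is

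d2 − b·d1,

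so the share of d2 lost is b·d1/d2. The documents give neither b nor d1/d2. The values below are assumptions.

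| d1/d2 | b = 0.3 | b = 0.5 | b = 0.7 |
|---|---|---|---|
| −0.25 | 7.5% gained | 12.5% gained | 17.5% gained |
| 0 | 0 | 0 | 0 |
| 0.25 | 7.5% | 12.5% | 17.5% |
| 0.5 | 15% | 25% | 35% |
| 1 | 30% | 50% | 70% |
| 2 | 60% | 100% | 140% (sign reversed) |

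Simulation agrees (3,000 runs per cell, three arms, both active drinks shifted equally against placebo, unit SDs so that b equals the correlation). At 6 per group, correlation 0.5 and d2 = 1, the mean estimates for d1 = −0.25, 0, 0.25, 0.5, 1 and 2 are 1.13, 1.01, 0.87, 0.76, 0.50 and 0.01. The formula gives 1.125, 1, 0.875, 0.75, 0.5 and 0.

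**Step 4: false positives if the drink acts only early (d2 = 0).** For d1 = 1 SD the false adjusted difference is −0.3, −0.5 or −0.7 SD at correlations 0.3, 0.5 and 0.7. Rejection by the nominal 5% F-test, at the 6 completers and the 10 recruits per group of section 17.2:

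| d1 | 6 per group (0.3 / 0.5 / 0.7) | 10 per group (0.3 / 0.5 / 0.7) |
|---|---|---|
| 0.25 SD | 4% / 5% / 5% | 5% / 5% / 7% |
| 0.5 SD | 5% / 7% / 11% | 6% / 9% / 16% |
| 1 SD | 6% / 11% / 26% | 9% / 18% / 46% |

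One-way ANOVA on the bout-2 slope stays at 4% to 5%.

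**The case against.** The strongest reply is that a bout-1 slope is implied. The Visit #3 text calls the final 30 minutes additional, which may mean in addition to a recording made during the two-hour rest. Section 6.5 does not limit the bout, and 17.1 presupposes a pretest. The design summary also lists sweat rate beside HRV, and sweat rate is measured around both bouts, so HRV's place in that list does not show it is bout 2 only. This stands as far as it goes: that the model cannot be run is one reading of an ambiguous text. It does not rescue the plan, because a bout-1 slope is recorded largely after the drink.

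The second reply is that a covariate measured after the drink is exposed to bias but not necessarily biased. Nothing in the documents says that the drink changes RMSSD within 30 minutes or how fast it is drunk. This is correct: with d1 = 0 there is no bias, and with d1 of 0.25 SD the error rate barely moves. The 26% and 46% figures are the top of an assumed range. But the documents do not establish d1 = 0, and the analysis should not depend on it.

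Third, HRV slope is a minor outcome. That is accepted and limits the weight of the point.

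**Conclusion.** The concern holds. No pre-drink HRV slope is scheduled at any visit, so the rule in 17.1 gives either a model without a covariate or adjustment for a measure the treatment may have changed. The first follows from the text alone if HRV is recorded only after bout 2. The second has unknown size and direction. Under the assumed values in Steps 3 and 4 it runs from no bias to a reversed sign, and from a 5% to a 46% false-positive rate. The fault is confined to HRV slope. It should be corrected before analysis, but it does not threaten the study's performance conclusions.

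**What to change.** In 17.1, exempt HRV slope from the pretest/posttest rule. Suggested default: *HRV recovery slope after the second bout will be compared between groups by one-way ANOVA; no first-bout HRV value will be used as a covariate.* In 6.5, state which bouts are recorded. Report any bout-1 slope as a separate post-drink outcome.

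The cost is one sentence in each section and possibly some precision. For an assumed 1 SD effect of both active drinks against placebo, simulated power is:

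| | ANOVA | ANCOVA, valid baseline, correlation 0.3 / 0.5 / 0.7 |
|---|---|---|
| 6 per group | 35% | 35% / 42% / 58% |
| 10 per group | 58% | 60% / 70% / 86% |

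If the sponsor wants a covariate, it must be named in advance and measured before the drink. Age and Visit #1 VO₂peak are already collected, but the documents do not show that either predicts HRV slope. An uninformative covariate costs a little power (about 34% against 36% at 6 per group).

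A like-for-like baseline would need a resting RMSSD before bout 1 or a slope after the Visit #2 bout. The latter looks feasible: warm-up and rest 3 + 2 + 1 + 3 = 9 min, intervals 5 × 4 = 20 min, separations 4 × 2 = 8 min, recording 30 min, in total 67 min plus TTE. For an assumed TTE of 2 to 10 min that is 69 to 77 min, before set-up and RPE teaching, against the 60 to 90 min in section 9.1. A cool-down before the recording would add 5 min. Its limit is that interval intensity is set from that familiarization trial, so the Visit #2 and Visit #3 bouts may differ.

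Separately, the cool-down in 6.4 and the immediate rest after bout 2 in 6.1 must be reconciled so that the RMSSD time points are consistent. This is common to all arms and does not bias the comparison between drinks.
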